8.4.3.2 Qualitative data collection

A subset of study participants will also be invited to participate in a semi-structured interview, so that more in-depth, qualitative engagement and user experience feedback can be collected. A topic guide will be developed to provide a framework for the interviews. Interviews will be conducted using video or call conferencing software and recorded for later transcription (if the participants consent). If they do not want the interview recorded, notes will be taken by hand and shared with the participant following the interview for verification. See 13.3 Appendix 3 for sample interview questions.

8.5 Data Analysis

8.5.1 Statistical Methods for Primary Outcome

Descriptive statistics will be used to characterise users, assess baseline comparability, and compare side effects. Primary comparisons between intervention and control groups will be conducted for primary and secondary outcomes. Primary analyses are designed with 80% power to detect a two-sided α of 0.05. All analyses will report 95% CI around estimate of effect. Comparative analyses will be conducted on an intention to treat basis, using linear or logistic regression, with adjustment for stratification variables.

We will explore missingness in our data, be that in relation to primary outcomes, follow-up data and in WYSA analytic information. The proportion of missing data will be explored and reported on descriptively. An hypothesised scenario, where patients remove themselves from the waiting list for treatment before the duration of follow-up may lead to missing data scenario. Currently, estimates

suggest that xxx% of our cohort will 'drop-off' waiting list before our primary endpoint. We will conduct exploratory sensitivity analyses in a complete case ('per protocol') cohort compared with the ITT analysis.

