Wysa will have two pathways to crisis alert and response. The first pathway is for patients to trigger the crisis response pathway by pressing a manual override button on the app. The second pathway is for the app to trigger the crisis response because of an individual's response to an outcome measure or the language used in free conversation with the AI. Because this pathway can be triggered by the app's natural language processing, the AI regularly checks in with the patient to ensure they are understanding them correctly.

When Wysa or the user triggers the crisis response pathway, users will be provided with a stepped crisis plan including grounding exercises, local crisis helplines, or a recommendation to attend A&E where there is significant injury or risk to life. Data will be collected indicating the number of false positives identified by the AI. Coinciding with this, the app pushes an update to the patient's linked electronic patient record through Mayden and sends an alert email to the 'Clinician of the Day' at each trust for human follow up.

[figure not shown]

Figure 2. High-level study Gantt chart

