Two questionnaires will be used to assess health-related quality of life: the EQ-5D-5L [40] and the Short Form 12 (SF-12) health survey [41]. The EQ-5D-5L provides a descriptive self-assessment of health in 5 dimensions: mobility, self-care, usual activities, pain/discomfort and anxiety/depression [40]. It is commonly used as a quality of life measure to conduct cost effectiveness analyses [42]. The EQ-5D-5L has a greater emphasis on physical than mental health, but has demonstrated the ability to capture changing anxiety severity [43]. The SF-12 survey is a reliable measure of functional health and is well-suited for this study, as it includes mental health items and has been shown to be acceptable for use as a screening tool for depressive disorders [44].

Cost-effectiveness

To conduct a health economic analysis, the study will collect data on health and social care service use, medication use and treatment costs, the implementation costs of Wysa, out of pocket medical expenses borne by patient and carers and productivity related costs such as work absence / time off work due illness. This data will be combined with the quality-of-life indicators to produce an assessment of the costs of adopting Wysa from the perspective of both the UK health and social care services and the wider society [45]. This analysis will also produce a budget impact model for each site that will be used to provide a final overall implementation strategy for more rapid adoption at other NHS sites and dissemination across the AHSN network in partnership with the new Integrated Care Systems. The team will also incorporate the environmental sustainability calculation in line with the Greener NHS agenda.

Table 6. Secondary Outcome Measurement

Secondary Outcome	Outcome Measure
Anxiety severity	
 Score on the GAD-7 [37]
Crisis identification	
 Number of users identified by the app for escalation of care compared to the number of patients in the control group who access A&E or out-of-hours services while waiting for treatment
Engagement	
 Uptake rates Dropout / 'did not attend' rates App usage data Qualitative feedback from semi-structured interviews
Acceptability	
 Qualitative feedback from semi-structured interviews Automated review questions periodically requested during general use of the tool

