8.3.1.2 Exclusion Criteria

- Patients ineligible for the standard IAPT care pathway;
- Patients with previous and current known major mental illness such as Schizophrenia, severe depression, any co-morbid neurological or neuro-psychiatric condition such as epilepsy;
- Patients with current psychosis or a history of psychotic symptoms within the last 6 months
- Patients with suicidal ideation;
- Patients scoring > 15 points on PHQ- 9;
- Patients scoring > 15 points on GAD- 7;
- Patients with significant cognitive disorders;
- Patients with noted neurodevelopmental conditions such as autism or ADHD;
- Patients previously diagnosed with a personality disorder;
- Patients who been under the care of CMHT or a specialised mental health services in the last 2 years;
- Patients who failed IAPT previously;

- Patients with referrals for specialist presentations of pre-existing, diagnosed conditions requiring a specialised assessment beyond the standard clinical pathway;
- Incapable of self-consent;
- In a dependent/unequal relationship with the research or care teams or any PPI representatives.

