8.3.3 Recruitment

8.3.3.1 Participant Identification

Participants who are referred, or refer themselves, to IAPT for mental health support (online or by phone) will be recruited from the three provider sites of the London Community Living Well Service, run by the Central North West London NHS Foundation Trust. The service receives on average 1100 referrals a month. All referrals will be screened by the psychology assistant against exclusion criteria and those eligible for the trial will be provided with information regarding the trial via email (see 13.1 Appendix 1). The psychology assistant will then contact participants to check further exclusion criteria not clear from service referral and to take informed consent. Screening will continue through the first 6 months of the intervention period, and we expect to be able to onboard significantly more individuals than our target sample size. All participants will have access to the Wysa app (including control participants who will receive access following the control period).

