8.4.3.1 Quantitative data collection

The quantitative outcome measures will be delivered directly to patients through the Wysa app or by Qualtrics survey (e.g. for participants in the control group). Participants in both conditions will complete four questionnaires at baseline and 3-months post-randomisation (PHQ-9, GAD-7, EQ-5D-5L, and SF-12). Outcome measures have been chosen that will not be a significant burden for participants to complete; none of the questionnaires are longer than 12 items or expected to take more than a few minutes each to complete. Together, the questionnaires should take participants from 10 to 20 minutes to complete. Patient responses will be automatically uploaded to the iaptus electronic patient records using the Mayden Prism API. App use data will be automatically stored through the app.

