- Acceptability of study: To ensure that there are no ethical concerns with the study that might have been overlooked by the researchers and that the design is participant-friendly, a local PPI group will be formed to collaborate with researchers throughout the study. For further details, please see the PPI section.

A comprehensive risk register and Hazard log is maintained by Wysa across its development as part of its Clinical Safety Management file. This risk register will be regularly reviewed and updated as part of the project management governance. Key risks for this project include:

- Clinical: A Structured What-IF Technique (SWIFT) analysis has been completed which highlighted that the main clinical risk of this project is unintended harm. This could be psychological or physical risk caused by unintended increase in psychological distress or the physical impact of increased reliance on screen time. We have mitigated the risk to patients by building a clinically underpinned crisis response pathway with handover capabilities to the clinical team at Central North West London NHS Foundation Trust.
- Excessive screen time: Health risks associated with excessive screen time are mitigated by ensuring that many of the strategies and skills taught by the app encourage users to complete them away from the screen. All risks and mitigations are outlined in the clinical safety management file.

- Technical: The main technical risk is that the system is not fully integrated with iaptus ready for our go live date, delaying the project. This is mitigated by completing planning works and scoping prior to the application for this award and for allowing contingency time in our project planning.
- Delays: A second risk is that information governance permissions are delayed or withheld at pilot sites - mitigated by a technical, security and privacy architecture that has already been approved by the representatives of the trust who are project partners on this award.
- Commercial: The need for good quality evidence combined with long sales cycle times in healthcare can produce a risk of limited cash flow - this is mitigated by Wysa's maturity as a company and track record of securing investment funding as needed. As a real-world use study the evidence generated by the project will help to respond to commissioners' need for a high quality evidence base, removing a core barrier to implementation.

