Real World Testing of an Artificial Intelligence-enabled App as an Early Intervention and
Support Tool in the Mental Health Referral Care Pathway

NCT05533190

8 August 2023

Methods

Randomisation – sequence generation

Demographic data was collected from all patients immediately after completion of the informed consent process, over the phone. Together with data from the IAPT referral, this information was used in the randomisation algorithm to ensure that the intervention and control arms were balanced on key variables (gender, age, ethnicity, self-reported antidepressant use, and severity of depression).

Randomisation – allocation concealment mechanism

Consenting participants were inputted into a masked computer randomisation algorithm and the outcome was recorded in an electronic record to conceal treatment allocation from study researchers. Participants were sent an automatic email to inform them of their group assignment, and participants in the intervention arm will receive the link to download Wysa.

Randomisation – implementation

Psychology assistants recruited specifically for the trial and covering the three London Community Living Well Service sites enrolled participants in the study. A computer generated the random allocation sequence assigned participants to interventions, with a ration of 2:1 randomization to the intervention group.

Blinding

Due to the nature of the intervention, no blinding of participants was possible in the study, as all participants knew whether they were using the app. Clinical treatment teams were not blinded as they knew through the electronic patient record if a participant has received the intervention. The evaluation team will be blinded to treatment using the randomisation algorithm.

Statistical methods

Descriptive statistics was used to assess baseline comparability and the distributions of the primary and secondary outcomes. Visualisations via density and box plots supplemented the tabulations. Linear regression was used to carry out comparative analysis of the primary outcome PHQ9, and secondary outcome GAD7, to compare the two treatment arms. For the primary outcome, PHQ9, the study was powered to detect a clinical meaningful difference of 2 points, with 80% power and a Type 1 error rate of 0.05. Additional post hoc regression was carried out for individuals who had a PHQ2<5 and PHQ2<4 at baseline.

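### The protocol promises to compare side effects but defines none, and its only between-arm crisis comparison counts a different thing in each arm, so no like-for-like harm estimate will result.

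*Protocol*

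**What the plan says.** Protocol section 8.5.1 lists the safety analysis in one clause: "Descriptive statistics will be used to characterise users, assess baseline comparability, and compare side effects". It gives no definition, source, recording method or time window.

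Section 9.1 reports a hazard analysis in which "the main clinical risk of this project is unintended harm", and includes a rise in psychological distress under that heading. What follows is mitigation, mainly the crisis pathway. The SPIRIT-AI checklist in Appendix 5 refers its harms item, which asks how adverse events will be collected and assessed, to this section.

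On data collection, section 8.4.3.1 says "Participants in both conditions will complete four questionnaires at baseline and 3-months post-randomisation", naming PHQ-9, GAD-7, EQ-5D-5L and SF-12. Section 8.2.5.2 adds crisis contacts taken from iaptus and service-use data for the economic analysis. Its Table 6 defines the crisis outcome as "Number of users identified by the app for escalation of care compared to the number of patients in the control group who access A&E"; for controls it also counts use of out-of-hours services.

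The SAP, under Statistical methods, says "Descriptive statistics was used to assess baseline comparability and the distributions of the primary and secondary outcomes", then describes regressions of PHQ-9 and GAD-7. Side effects do not appear.

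**The concern.** A promised safety comparison needs a variable measured the same way in both arms. The text available for review designates none. The analysis that looks closest to one, crisis identification, draws on a different source in each arm.

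Section 10.1 says the data will support a Class IIa regulatory submission and wider adoption. A reader of the results would want to know whether some users got worse, which is the risk the trial's own hazard analysis puts first. A mean PHQ-9 difference can favour the app while a minority deteriorates. The monitoring group's review under section 9.8 is affected too, because it is given no named harm variable to look at.

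**Working it through.** **1. Can the crisis outcome serve as the harm comparison?**
- Wysa arm: the count is of app flags. Section 6 gives a manual button as one route to a crisis alert and, as the other, "The second pathway is for the app to trigger the crisis response because of an individual's response to an outcome measure" or to language used in conversation.
- Control arm: the count is of contacts with A&E, the crisis helpline or out-of-hours services.
- Controls cannot generate app flags before the endpoint. Section 8.3.3.1 says "All participants will have access to the Wysa app (including control participants who will receive access following the control period", and the GP letter in Appendix 4 puts that at 3 months.

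One count reflects the app's detection and the other reflects service use. A difference between them could arise with no harm, and no difference could hide harm. Section 8.2.5.2 itself presents this outcome as a measure of the app's ability to identify crises.

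**2. What is held in both arms?** PHQ-9 and GAD-7 at baseline and 3 months (section 8.4.3.1). Worsening can therefore be computed for each participant with both scores.

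**3. The plan's own sample size (section 8.3.2.1).** Inputs: difference 2, SD 6.6, two-sided alpha 0.05, power 80%, 2:1.
- Smaller arm = 1.5 × (1.96 + 0.8416)² × 6.6² / 2² = 128.2, rounded up to 129. Total 3 × 129 = 387.
- With SD 6.66, also given in that section, the smaller arm is 131 and the total is 393, the stated figure.
- Completers: 480 × 0.8 = 384, or 128 and 256 at 2:1.

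**4. Precision of a both-arm event comparison.** Half-width = 1.96 × √[p(1 − p)(1/128 + 1/256)], with the same event rate p in both arms. Here 1/128 + 1/256 = 0.01172.

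| Event rate p | Source | Half-width (percentage points) |
|---|---|---|
| 1% | assumed | 2.1 |
| 5% | assumed | 4.6 |
| 10% | assumed | 6.4 |
| 11% | A&E figure in section 7.1 | 6.6 |

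At 10%: 1.96 × √(0.09 × 0.01172) = 0.064. The documents give no deterioration rate. The 11% is a survey figure for people waiting for treatment and may not fit this lower-severity sample. At 1% only one or two events are expected in the smaller arm, so an exact method would be needed.

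At an 11% control rate, 80% power needs about 22% in the app arm.

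The protocol allocates 2:1 towards usual care and the SAP 2:1 towards the intervention. They must be reconciled, but the half-width is the same either way.

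**5. Missing scores.** Suppose 20% are missing in each arm and 10% of completers worsen. The rate among all randomised then lies between 0.8 × 10% = 8% (no missing participant worsened) and 8% + 20% = 28% (all did). The extreme risk differences are −20 and +20 points, well beyond the 6.4-point sampling half-width.

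**The case against.** The strongest reply is that the plan has several ways of seeing harm. This is largely right, and it rules out stronger readings.

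- A reader might infer that app alerts are the only harm signal, or that there are no control-arm data. That holds for app alerts alone. Section 8.2.5.2 names iaptus crisis contacts and service use, and four questionnaires are taken in both arms.
- A reader might infer that side effects means app alerts. Section 8.5.1 does not say so, and section 8.2.5.2 uses the flags for crisis identification.
- A reader might infer that the trial cannot tell whether the app makes people worse. The PHQ-9 test is two-sided, so average harm is detectable. Section 8.5.2 plans differential effects by age, severity and app use, and section 9.8 allows a pause for unforeseen risks. What is missing is a rate of individual deterioration by arm.
- A reader might conclude that no side-effect data are collected at all. The data-collection figure is not shown and the clinical safety management file lies outside these documents, so the most that can be said is that the available text states no such collection.
- It is tempting to add a PHQ-9 self-harm item, since "Patients with suicidal ideation" are excluded at entry. The documents specify only the PHQ-9 score and do not describe its items or say how ideation is screened, so this is not proposed.

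Two objections limit the remedy. Section 8.2.5.2 does not say that iaptus contacts will be extracted for the app arm. Also, the app can recommend A&E and alert clinicians (section 6), so contacts may differ by arm without any harm.

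**Conclusion.** The concern holds in this form. The side-effect comparison cannot be made as specified, because the available text defines no side effect and gives no recording method, the checklist's harms reference leads to risks and mitigations only, and the SAP omits the comparison. The crisis outcome does not fill the gap, because its two arms count different things.

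The gap can be closed with scores already collected. Precision would be moderate: about ±4.6 percentage points at 5%, ±6.4 at 10% and ±6.6 at 11%, assuming 384 completers at 2:1 and equal rates in both arms. That is enough to describe deterioration if it is fairly common, but too little to rule out a modest excess of rare events. Missing 3-month scores could matter more than sampling error.

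This should be changed, but it does not undermine the primary analysis.

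**What to change.** In protocol section 8.5.1, replace the side-effects clause with a harm outcome defined identically in both arms, and name it in the SAP.

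- **Lead outcome:** the proportion whose PHQ-9 or GAD-7 score worsens from baseline to 3 months by an amount the clinical team sets in advance.
- **Analysis:** risk differences with 95% CI by randomised arm, a stated method for missing 3-month scores, and a sensitivity analysis that lets those missing have worse outcomes.
- **Supporting outcome:** iaptus crisis-line and A&E contacts over the same period, counted the same way in both arms, if they can be extracted for the app arm. Interpret them cautiously, because the app can itself prompt such contacts. Report app flags separately as a description of the app arm.
- **Status:** the SAP is dated 8 August 2023 and written largely in the past tense. If outcome data have been seen, label these analyses post hoc.

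The questionnaire outcome costs some wording, a clinical decision on the threshold and a few tables, with no new instrument or visit. The iaptus outcome may need a data extract for the app arm.

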8.3.2 Sampling

8.3.2.1 Sample Size

Approx 1100 eligible patients are seen per month at the IAPT in the CNWL NHS Foundation Trust. Preliminary work suggests that Wysa is associated with a mean clinical improvement in PHQ-9 of 5.84 (SD6.66) [28]. This study is powered to detect a clinically meaningful effect on the PHQ-9 scale [28]. Based on a SD of 6.6 and a 2:1 recruitment ratio (usual care: intervention) a sample size of 393 would allow detection of a difference in PHQ-9 of at least 2 points, with 80% power. Augmenting the sample size to 480 would allow for 20% attrition, whilst still maintaining sufficient power to detect clinically and statistically meaningful differences with a Type 1 error rate of 0.05. This inflated sample size would also allow for adjustment for stratification variables, gender, age, ethnicity, self-reported antidepressant use, and severity of depression.

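### The planned models leave out each secondary score's own baseline (GAD-7, EQ-5D-5L, SF-12), which costs precision; for PHQ-9 the severity covariate is undefined rather than shown to be missing

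*Protocol*

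**What the plan says.** Protocol section 8.5.1 sets the comparisons for primary and secondary outcomes on an intention-to-treat basis, "using linear or logistic regression, with adjustment for stratification variables". Section 8.3.2.1 gives the set: "adjustment for stratification variables, gender, age, ethnicity, self-reported antidepressant use, and severity of depression". Section 8.4.1.1 names the same five as the balancing factors in the randomisation. Neither section states the instrument, scale or cut-points behind severity of depression.

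Section 8.4.3.1 says "Participants in both conditions will complete four questionnaires at baseline and 3-months post-randomisation (PHQ-9, GAD-7, EQ-5D-5L, and SF-12". The exclusion criteria in 8.3.1.2 include "Patients scoring > 15 points on GAD- 7", with the same limit for PHQ-9, so a score on both scales should exist before randomisation.

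Section 8.5.2 adds covariates only in secondary analyses, and only for factors that look imbalanced at baseline. The SAP, under Statistical methods, names linear regression for PHQ-9 and GAD-7 and no covariate. It describes no EQ-5D-5L or SF-12 model.

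**The concern.** A patient-reported score at baseline is usually one of the best predictors of the same score at follow-up. Neither document puts baseline GAD-7, EQ-5D-5L or SF-12 into the model for its own 3-month value. The imbalance rule in 8.5.2 does not fill the gap: it depends on the data, whereas own-baseline adjustment improves precision whether or not an imbalance is seen.

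What is at stake is the width of the confidence intervals for these three outcomes. GAD-7 matters most, being the anxiety outcome and the only secondary outcome that the SAP models. For PHQ-9 the question is what severity of depression means in the model.

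**Working it through.** **1. The plan's own figure.** The inputs are "Based on a SD of 6.6 and a 2:1 recruitment ratio (usual care: intervention) a sample size of 393", a "difference in PHQ-9 of at least 2 points, with 80% power" (8.3.2.1), and two-sided α of 0.05 (8.5.1).
- Smaller arm = 1.5 × [6.6 × (1.960 + 0.842) / 2]² = 128.2, so 129. Total = 129 + 258 = 387, within 1.5% of the stated 393.
- With SD 6.66, the value quoted beside the preliminary improvement, the total is 131 + 262 = 393 exactly.
- With 20% attrition, 480 × 0.8 = 384 evaluable, and power is 79.9% (SD 6.6).

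The calculation is for an unadjusted comparison of two means, so the sample size does not depend on baseline adjustment. The 2:1 ratio favours usual care in the protocol and the intervention in the SAP; this does not alter the total.

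**2. GAD-7.** The reference model already contains depression severity, so the gain is what baseline GAD-7 adds beyond it. For this step severity is treated as the baseline PHQ-9 score. Write o for the correlation of baseline with 3-month GAD-7, c for that of baseline PHQ-9 with 3-month GAD-7, and b for that between the two baselines. Then:

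proportional cut in residual variance = (o − c·b)² / [(1 − b²)(1 − c²)]

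The documents give no correlations. Assumed ranges are o 0.5-0.6, c 0.3-0.4, b 0.5-0.7.
- Smallest gain (o 0.5, c 0.4, b 0.7): 0.22² / (0.51 × 0.84) = 0.113. Interval width × √0.887 = 0.942, about 6% narrower.
- Largest gain (o 0.6, c 0.3, b 0.7): 0.39² / (0.51 × 0.91) = 0.328. Interval width × √0.672 = 0.820, about 18% narrower.

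**3. EQ-5D-5L and SF-12.** A gain is expected in the same way, but the documents offer nothing from which to size it.

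**4. PHQ-9.** Let r be the correlation of baseline with 3-month PHQ-9 (assumed 0.3-0.7), and k the share of the baseline score's variance that the severity covariate retains. The further cut from using the continuous score is 1 − (1 − r²)/(1 − k·r²). Entry is capped at 15, so k was computed over 0-15 for three assumed score distributions.

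| How severity enters | k | Further cut, r = 0.3 | r = 0.5 | r = 0.7 |
|---|---|---|---|---|
| Continuous PHQ-9 score | 1 | 0 | 0 | 0 |
| Bands 0-4 / 5-9 / 10-14 / 15 (assumed) | 0.78-0.91 | 1-2% | 3-7% | 8-17% |
| Single cut at 10 (assumed) | 0.66-0.71 | 3% | 9-10% | 22-25% |
| No covariates, as the SAP reads | 0 | 9% | 25% | 49% |

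At r = 0.5, a 3-7% cut narrows the interval by about 1.5-3.5%, and a 9-10% cut by about 5%. Power at 384 evaluable with r = 0.5 is about 88-89% with the four bands, about 87% with the single cut and 89.8% with the continuous score. With no covariates it stays at 79.9%, against 83.5%, 89.8% and 97.5% with the continuous score at r = 0.3, 0.5 and 0.7. These powers take 6.6 as the SD of the 3-month score.

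**The case against.** A reader might infer that the primary analysis discards the baseline PHQ-9. The documents do not support that. Severity of depression is in the protocol's adjustment set and may be the PHQ-9 score itself.

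A reader might also credit GAD-7 with the full squared own-correlation, 25-36% on the range assumed here. That measures the gain against a model with no useful baseline covariate, whereas the protocol's model already holds depression severity.

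Nor does every secondary interval suffer: engagement, acceptability and crisis identification have no baseline score of their own. The remark in 8.5.2 about unpowered analyses concerns the secondary analyses described there, while 8.5.1 places secondary outcomes among the primary comparisons. Section 8.5.2 also offers some correction for visible imbalance. No bias follows, and the stated sample size holds without baseline adjustment. All of this stands.

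The most important objection is to the remedy. Under 8.4.1.2 the app link is sent with notice of allocation, and under 8.4.3.1 questionnaires come through the app or by Qualtrics. Some baseline EQ-5D-5L and SF-12 scores may therefore be taken after allocation, by a different mode in each arm, and be missing for people who never install the app. Adjusting for such scores could damage the randomised comparison. This limits the fix, but not for PHQ-9 and GAD-7 if the eligibility scores are used.

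Finally, the SAP is dated 8 August 2023 and describes its regressions in the past tense, so a new covariate may be a post hoc change.

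**Conclusion.** The point holds for GAD-7, EQ-5D-5L and SF-12: each is collected at baseline, and neither document places it in its own model. It is a loss of efficiency. For GAD-7 the loss is about 11-33% of residual variance, or intervals that could be about 6-18% narrower, entirely on the assumed correlations. For EQ-5D-5L and SF-12 it is unquantified, and the timing of their baselines is unclear.

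For PHQ-9 the fault is an undefined covariate, plus a SAP that does not repeat the protocol's adjustment. The precision at stake runs from none to modest under the protocol's model with a score or several bands. It becomes larger only with a coarse split and a high correlation, and reaches the full squared correlation only if the SAP model is run with no covariates.

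**What to change.** In protocol 8.5.1 and in the SAP, state that each continuous 3-month outcome is analysed by linear regression on arm, the stratification variables and the same outcome's pre-randomisation score as a continuous covariate. Define severity of depression as the eligibility PHQ-9 score, so that it serves both as the stratification covariate and as the PHQ-9 baseline. Use the eligibility GAD-7 score in the GAD-7 model. Add baseline EQ-5D-5L and SF-12 to their own models only once it is confirmed that they were completed before allocation in both arms. Have the SAP list the full covariate set so that the two documents agree.

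For PHQ-9 and GAD-7 this costs a short edit and no new data, provided that the eligibility scores were retained. For EQ-5D-5L and SF-12 it also needs a check of completion dates against randomisation dates. If the outcome data have already been analysed, report the adjusted model beside the original and label it as added after the original analysis.
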